Between August 2015 and August 2016, we screened patients with acute traumatic cervical SCIs (GOSCIP study; clinical trials NCT02524379) for potential treatment with Cirara™. Sixteen patients were screened during this period but none met the eligibility criteria. Given the ongoing enrolment difficulty with this intravenous drug within the 6 hr timeline, we have decided to amend several elements of the trial including some of the inclusion/exclusion

criteria. First, the route of administration will be changed to the oral form allowing for easier and streamlined drug administration. An extension of the window of administration to 8 hours from the time of injury will also be implemented. Several screened patients fell out of the eligibility due to this constrained time window, especially considering that Cirara™ preparation takes in the order of 1-2 hours.

The feasibility of screening, consenting, enrolling, and administering oral glyburide in the acute setting following spinal cord trauma (≤ 8 hours from injury) will be assessed at the participating centers. Further, a comprehensive assessment of all-cause AEs will be undertaken in this study for spinal cord trauma patients.

The data obtained from this pilot study should inform the design of further multicenter phase II/III clinical studies evaluating the efficacy and safety of oral glyburide in improving functional outcomes following SCI.

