3.0 OBJECTIVES

3.1 Primary Objectives

- **Feasibility:** To assess the feasibility of running a larger phase II or III study among this population of patients where treatment must begin within a defined time frame. The number of patients who would otherwise be eligible for the study but did not receive study treatment within the 8-hour time frame will be recorded (ratio of recruited versus screened). The rate of recruitment will also be recorded.
- **Safety:** Vital signs, clinical exams, ECG, and clinical laboratory results will be carefully and continuously monitored during the course of hospitalization. Adverse events (AEs) will be assessed throughout the course of hospitalization through Day 28. In addition to presenting a summary of all AEs, where possible, a comparison of AEs occurring in study subjects vs. those occurring in matched historical controls (as captured in the NACTN registry) will be made. To facilitate this comparison, AEs will be grouped into one of 10 systems according to a modified NACTN chart [20, 21] (see appendix 1): cardiac, pulmonary, hematology, gastrointestinal/genitourinary, infections, skin, failure of stabilization, neuropsychiatric, hypoglycemia/other metabolic, and other. These AEs will be described further with respect to the specific name of the event (that is, the “type” of event; for example, for cardiac events, the type could be bradycardia or other dysrhythmia, cardiac arrest, etc.). Severity (“intensity”, as per the NACTN chart) as well as relatedness to glyburide will also be assessed. The frequency of AEs, as well as mortality (all-cause and cardiac-related), will be compared to that of a matched cohort from the NACTN registry [20, 21].

Specific outcome variables related to assessing blood glucose (BG)-related safety of glyburide are:

- Hypoglycemia (i.e. Blood Glucose (BG) < 55 mg/dL
- Symptomatic hypoglycemia i.e. hypoglycemia with investigator-identified hypoglycemic symptoms.

The following table defines which BG values should be reported as AEs:

Table 1: Blood Glucose Values and AE reporting

BG Value	Report as AE?
70-79 mg/dL	Mandatory AE reporting not required; may be reported as an AE (and coded appropriately in terms of severity) if the event meets the protocol-defined definitions.
55- 69 mg/dL	Must be reported as an AE, if confirmed by a point-of-care or lab value retest (and coded appropriately in terms of severity)

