4.0 STUDY DESIGN

4.1 Inclusion/Exclusion Criteria

All patients with ASIA A, B or C acute traumatic spinal cord injuries will be assessed for suitability and prospectively enrolled in the study. Only cervical level (C2-C8) level injuries in patients aged 18 to 80 years old will be included. Detailed eligibility criteria are listed below.

The use of immunosuppressive therapy (including methylprednisolone and other corticosteroids) will be discouraged; however, use of such therapy will not require exclusion or discontinuation from the study. While once considered as an option for patients with acute SCI, it is noteworthy that more recent recommendations have all re-

evaluated the routine use of methylprednisolone [28]. The most recent guidelines published by a panel convened by the Joint Section on Spine and Peripheral Nerves of the American Association of Neurological Surgeons and Congress of Neurological Surgeons has in fact recommended against its use following acute SCI given its negative risk- benefit profile [3]. In the words of the panel: “Administration of methylprednisolone for the treatment of acute SCI is not recommended. Clinicians considering methylprednisolone therapy should bear in mind that the drug is not approved by the Food and Drug Administration for this application. There is no Class I or Class II medical evidence supporting the clinical benefit of methylprednisolone in the treatment of acute SCI. Scattered reports of Class III evidence claim inconsistent effects likely related to random chance or selection bias. However, Class I, II, and III evidence exists that high-dose steroids are associated with harmful side effects, including death.” Of note, the recent phase 1/2a riluzole study reported that corticosteroids were administered at the time of admission to only 39% of the patients (while 58% of historic NACTN registry patients had received this treatment) [4].

- **Inclusion Criteria:**

1. Age: ≥ 18 years and ≤ 80 years
2. Written informed consent by patient or legal authorized representative
3. No other life-threatening injury
4. No evidence of sepsis
5. Acute cervical SCI with ASIA Impairment Scale grade A, B or C on admission
6. Non-penetrating SCI at neurologic level from C2 to C8
7. Initiation of study drug within 8 hours of injury

- **Exclusion Criteria**

1. Unconsciousness or other mental impairment that prevents neurological assessment within the first 8 hours
2. Acute SCI with ASIA Impairment Scale grade D or E

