4.2 Number of Patients

To assess the feasibility of recruitment and of the protocol procedures (specifically the ≤ 8 hr injury-to-drug timeframe), the study will plan to enroll and treat 10 patients across all study sites.

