7.0 STATISTICAL CONSIDERATIONS

Descriptive statistics will be generated for all variables of interest. Categorical measures will be reported with frequencies and percentages and continuous measures with means and standard deviations. The frequency of AEs will be reported (as captured on the modified NACTN form) and, where possible, will be compared to those of the matched controls (along with corresponding confidence intervals). We will match study patients and the historical NACTN cohort data on criteria including: age, co-morbidities, injury level, and injury severity (ASIA A, B or C SCI). Additionally, the number of patients who were otherwise eligible for the study but did not enroll due to lack of infusion within 6 hours will be reported. Secondarily, matched tests will be utilized to compare neurologic outcomes between those receiving glyburide and matched historical controls.

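### Section 7.0 reports the time-window count on an infusion and 6-hour basis and by non-enrolment, contradicting the 8-hour, not-treated count under the primary feasibility objective in Section 3.1

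*Combined protocol and SAP*

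**What the plan says.** Section 7.0 contains one sentence specific to feasibility. It undertakes to report the "number of patients who were otherwise eligible for the study but did not enroll due to lack of infusion within 6 hours".

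Section 3.1, under the primary Feasibility objective, describes the corresponding count as patients who would "otherwise be eligible for the study but did not receive study treatment within the 8-hour time frame will be recorded". It adds a bracketed reference to the ratio of recruited to screened patients and says that the recruitment rate will also be recorded.

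Inclusion criterion 7 in Section 4.1 is "Initiation of study drug within 8 hours of injury". Sections 1.1, 1.2, 4.2, 5.2, 5.3, 5.5 and 5.8 also use 8 hours, and the drug under study is oral.

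Section 2.0 describes an earlier study of an intravenous preparation and gives the reason for changing it: "Given the ongoing enrolment difficulty with this intravenous drug within the 6 hr timeline". It then reports a change to the oral route and says: "An extension of the window of administration to 8 hours from the time of injury will also be implemented".

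Section 9.1 lists, among the reasons for discontinuation, a subject who enrols but gets no study drug because time ran out. It requires the reason to be entered in the case report form.

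**The concern.** Whether treatment can be started inside the window is a primary question here. Section 4.2 says the 10 patients are enrolled "To assess the feasibility of recruitment and of the protocol procedures", and names the 8-hour injury-to-drug interval in particular. The history makes the count informative. In the earlier study, "Sixteen patients were screened during this period but none met the eligibility criteria", and "Several screened patients fell out of the eligibility due to this constrained time window". The number of otherwise eligible patients lost to the new window is a natural gauge of whether the extension helped. Section 5.3 also cites a median injury-to-drug time of 8.5 hours in the riluzole study. The protocol attributes that to additional MRI, which this trial does not require before dosing, so the figure does not carry over directly. It does show that losses to an 8-hour limit are a practical possibility.

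Against that background, the only feasibility item in the full statistical section describes a different route and a different limit, and counts a different status. Two operative definitions stand side by side, and no clause says which governs.

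**Working it through.** The plan gives no figure to reproduce, and the documents contain no injury-to-drug times for this trial. The check is therefore a comparison of definitions.

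| Element | Section 7.0 | Section 3.1 | Rest of protocol |
|---|---|---|---|
| Route | Infusion | Study treatment | Oral (1.1, 2.0, 5.3) |
| Limit from injury | 6 hours | 8 hours | 8 hours (1.1, 1.2, 4.1, 4.2, 5.2, 5.3, 5.5, 5.8) |
| Status counted | Not enrolled | Not treated in time | Enrolled but undosed patients foreseen (9.1) |

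**Route and limit.** Nobody in this trial receives an infusion, and no eligibility rule closes at 6 hours. Section 2.0 attaches both terms to the earlier study and says both were changed. Carry-over is the likely origin, though that is an inference. The study calendar's column heading of up to 6 hours does not support Section 7.0: it is a screening interval counted back from treatment, not a limit counted from injury.

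**Status.** Divide the otherwise eligible patients who miss the window into three groups:

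- N: not enrolled because the drug could not be started in time.
- E: enrolled, but not dosed for lack of time (the Section 9.1 case).
- L: enrolled and first dosed after 8 hours (a protocol deviation).

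Then:

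- Section 3.1, read literally, counts N + E + L. It asks only whether treatment was received within 8 hours and states no cause.
- Section 7.0, with route and limit aligned but its non-enrolment condition kept, counts N.
- Difference: (N + E + L) − N = E + L.

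So correcting only the route and the hours would leave the two sections apart by E + L.

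**Patients dosed between 6 and 8 hours.** They are enrolled, so Section 7.0 does not count them. They are treated inside 8 hours, so Section 3.1 does not count them either. Their contribution is 0 to both.

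**Size.** The documents give no value or range for N, E or L. The only related figures are 16 screened and 0 eligible in the earlier study, and neither says how many patients will miss the present window.

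**Reach.** Section 1.4 names the primary feasibility outcomes as the recruitment rate and the proportion recruited of those screened. Neither uses a 6-hour limit. Section 4.2 gives the planned 10 patients without a calculation, and no test depends on this count.

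**The case against.** The strongest reply is that this is leftover wording with little practical consequence. Section 3.1 already commits the trial to recording the 8-hour number, the 8-hour limit recurs throughout, and Section 7.0 promises descriptive statistics for all variables of interest. An analyst is unlikely to apply a 6-hour infusion rule to an oral drug. Much of this stands, and it limits the point to one descriptive count. It does not settle the status question: nothing in Section 7.0 tells the analyst whether an enrolled but undosed patient belongs in the count.

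A second reply is that Section 3.1 is itself not fully explicit. Its bracketed reference to recruited versus screened patients leans towards recruitment status, so N + E + L is a literal reading rather than a stated formula. That is fair. The status difference is therefore less certain than the conflict over route and limit.

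A reader might go further and infer that the Section 7.0 count cannot be applied at all, because enrolment precedes dosing and so a missing dose could never prevent enrolment. The documents do not support this. Inclusion criterion 7 makes timely initiation a condition of eligibility, and Section 5.1 allows enrolment only once the criteria are met. A patient who plainly cannot be dosed in time therefore fails eligibility and is not enrolled. That is group N, which the sentence evidently aims at.

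A reader might also infer that patients dosed between 6 and 8 hours would be reported as failures. They would not, because they are enrolled.

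**Conclusion.** The contradiction is real and stands in current text. Section 7.0 names a route and a limit that do not belong to this trial as described everywhere else, and its status condition is narrower than that of the primary feasibility objective it serves. Route and limit are certain from the text. The status difference rests on reading Section 3.1 as written, by treatment received and not by enrolment.

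The consequence is one descriptive feasibility count that could be reported short by E + L, a number the documents do not allow anyone to estimate and which may be zero. The recruitment rate, the recruited-to-screened proportion and the safety and neurological comparisons are untouched. The point should be corrected before reporting, because the count bears on a primary objective and the correction is nearly free. It does not threaten the design.

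**What to change.** Replace the Section 7.0 sentence with one in Section 3.1's own terms, keeping its phrase "otherwise be eligible for the study but did not receive study treatment within the 8-hour time frame will be recorded" but with the final word changed from recorded to reported. Avoid adding a causal condition in Section 7.0 alone. Section 3.1 has none, and a clause limited to patients who never received a first dose could drop someone first dosed after 8 hours, creating a third definition.

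Report the total in two parts: those not enrolled, and those enrolled but not treated in time. The split removes the ambiguity over status and shows whether losses occur before or after enrolment.

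The cost is one sentence and a simple split. No new data item appears to be needed. Section 3.1 already undertakes to record the number, Section 9.1 puts the reason for discontinuation in the case report form, and the time of injury and start time of drug are already collected under Sections 5.1 and 5.8.

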8.0 DATA SAFETY MONITORING PLAN

The data and safety monitoring plan will involve the continuous evaluation of safety, data quality and data timeliness. Investigators will conduct continuous review of accrual and patient safety. The frequency and severity of AEs will be reviewed by the PI and compared to other sources, including published literature and scientific meetings. SAEs will also be reviewed by the Data and Safety Monitoring Committee (DSMC). The PI in conjunction with the DSMC will determine if the trial should be terminated early based on the AE reviews.

The DSMC will consist of an ethicist, an independent biostatistician and an independent clinician with specialty in neurologic surgery. The DSMC will meet prior to study initiation and on accrual of every 3 patients (but at a minimum of twice a year). DSMC meetings will be scheduled within a month of every 3rd patient being enrolled in the study. Prior to each scheduled DSMC meeting, the PI will prepare a progress report that will be reviewed by the DSMC.

9.0 STUDY CONDUCT CONSIDERATIONS

9.1 Regulatory and Ethical Consideration (including the informed consent process)

Subject Withdrawal

Subjects may voluntarily withdraw from the study at any time for any reason, and without prejudice to further treatment. Subject participation in the study may be terminated at any time at the discretion of the Investigator.

Possible reasons for discontinuation include, but are not limited to, the following:

- The subject's health would be jeopardized by continued participation (e.g., the patient required restricted medication, or alternative treatment seems to be in the subject's best interest.)
- Occurrence of a significant or intolerable clinical or laboratory AE that, in the opinion of the investigator, requires early termination.

- Withdrawal of subject consent. Subject withdrawal may occur any time the subject wishes to no longer continue with the study. Every attempt must be made to obtain information about the reason(s) for discontinuation, and any possible adverse events.
- Subject is enrolled but does not receive study drug, due (for example) to insufficient time to prepare and administer study drug, or elevated liver enzymes at screening.

The date the subject is discontinued from the clinical investigation and the reason for discontinuation will be recorded in the case report form (CRF). Subjects whose study therapy is discontinued for any reason should be treated and followed according to established medical practice.

Note that if a site learns, while a patient is receiving Study Drug, that the patient had taken sulfonylureas within 7 days of study enrollment, this will not be a cause for automatic discontinuation of Study Drug, or of withdrawal from the study.

Project Management

OSU Coordinating Center will be responsible for project management of the Study.

Data Management

Data entry will occur at the enrolling sites using the electronic data capture system (REDCap). Data quality assurance and analyses will be performed by the OSU Coordinating Center.

Data Monitoring

All aspects of the study will be monitored at regular intervals by qualified individuals from the OSU Coordinating Center. Monitoring will be conducted in accordance with FDA and International Conference on Harmonization (ICH) Good Clinical Practice (GCP) guidelines, and will be described in a Data Monitoring Plan. The investigators must agree to allow monitors, FDA, or other relevant health authorities to inspect facilities and records relevant to this study.

Institutional Review Board (IRB) Review and Informed Consent

This protocol and the informed consent document and any subsequent modifications will be reviewed and approved by the IRB or ethics committee responsible for oversight of the study. A signed and dated consent form will be obtained from the subject.

Record Retention

Investigators must retain all study records required by the applicable regulations in a secure and safe facility. All records are to be retained by the Investigator for at least 2 years after the United States Food and Drug Administration/local health authority approves the New Drug Application (NDA); or a minimum period of 2 years following the termination or withdrawal of the health regulatory agency exemption (e.g., Investigational New Drug (IND) or clinical trial application) under which the study was conducted, or for a period consistent with the record retention policies of the country where the study is being conducted.

Subject Confidentiality

All laboratory specimens, evaluation forms, reports, and other records that leave the site will be identified only by the Study Patient Number (SPN) to maintain subject confidentiality. All records will be kept in a locked file cabinet. All computer entry and networking programs will be done using SPNs only. Identifiable clinical information will not be released without written permission of the subject, except as necessary for monitoring by the IRB, the FDA, or other relevant health authority representative.

Study Modification/Discontinuation

The study may be modified or discontinued at any time by the PI, IRB, the FDA, or other government agencies as part of their duties to ensure that research subjects are protected.

9.2 Publication Policy

Publications and oral presentations of any results from the study shall be in accordance with accepted scientific practice, academic standards and customs and in accordance with the specific policy developed for the study.

10.0 CONCLUSION

In summary, this is a small and open-label study by design, therefore necessitating cautious interpretation. However, the study's findings may provide invaluable data on glyburide's safety and pharmacokinetic profile as well as preliminary data on its ability to improve neurologic outcomes following SCI. Taken together, this data will allow for a more rational subsequent phase II/III trial design.

APPENDIX 1: Modified NACTN Chart

See attached document

APPENDIX 2: SAE Case Report Form

See attached document
